15.2.3 Outcome

The outcome of each AE must be assessed according to the following classifications:

Table 6: Adverse Event Outcome Classifications

Classification		Definition
Resolved without sequelae		Subject fully recovered with no observable residual effects
Resolved with sequelae		Subject recovered with observable residual effects
Ongoing	Improved	Subject's condition improved, but residual effects remain
	Unchanged	AE is ongoing without changes in the overall condition
	Worsened	Subject's overall condition worsened
Death		Subject died as a result of the AE (whether or not the AE is related to the device or procedure)

15.2.4 Expectedness (Anticipatedness)

An anticipated AE is an effect which by nature, incidence, severity or outcome has been identified as a possible complication associated with the investigational medical device and/or intervention procedure.

Potential AEs that are reasonably anticipated to occur during the cardiac EP procedure are listed in table 7. These events should be reported via EDC as anticipated AEs. Anticipated AEs are to be reported to the sponsor via EDC as indicated in section 15.4.

Table 7: Comprehensive List of Anticipated Adverse Events

Anticipated Adverse Events	
(Acute) renal failure	Hypoxia
(Aspiration) pneumonia	Increased phosphokinase level
(Skin) laceration	Infection, localized
(Vascular) bleeding	Infection, systemic
Acute Respiratory Distress Syndrome (ARDS)	Ischemia
Air embolism	Local Hematoma/ecchymosis
Allergic reaction to contrast media	Localized skin reaction
Allergic skin reaction	Mitral Insufficiency
Altered Mental Status Confusion; Altered Level of Consciousness;	Myocardial infarction with or without ST elevation
Anemia	Nausea
Anesthesia complications/reactions	Palpitations
Anoxic or hypoxic encephalopathy	Papillary Muscle tear/injury
Aortic Puncture	Pericardial effusion resulting in tamponade
Apnea - sedation induced	Pericardial effusion without tamponade
Arrhythmia (new or worsening of pre-existing arrhythmia)	Pericarditis
Asymptomatic Cerebral Emboli	(Periesophageal) vagal nerve injury
Atelectasis	Peripheral nerve injury
Atrial fibrillation	Phlebitis
Atrial Septal Defect (acquired)	Phrenic nerve damage/injury
Atrio-Esophageal fistula and/or injury	Pleural effusion
AV fistula	Pneumothorax
Back Pain	Post- and perioperative pain
Bronchial fistula, Broncho-pericardium fistula	Post Procedural Hematuria
Cardiac arrest	Pseudoaneurysm
Cardiac pacemaker insertion or replacement	Pulmonary edema
Cardiac perforation	Pulmonary embolism
Cardiac Tissue Injury	Pulmonary hypertension
Cardiac Valve Rupture/Damage	Pulmonary toxicity, like acute pulmonary syndrome
Cardiogenic Shock	Pulmonary vein dissection
Cerebro-Vascular accident (CVA)/Stroke	Pulmonary vein stenosis
Chest pain/discomfort	Renal Artery Stenosis
Complete or incomplete heart block	Respiratory arrest
Conduction block	Respiratory depression
Coronary Artery Stenosis	Respiratory failure
Coronary artery thrombosis	Respiratory infection
Death	Retinal Artery Embolism

Deep venous thrombosis	Retroperitoneal bleeding
Diaphragmatic paralysis	Sepsis
Dislodgement/Malfunction of pacemaker/defibrillator leads	Sinus bradycardia
Disseminated Intravascular Coagulation	Sinus tachycardia
Dizziness, presyncope, vertigo	Skin burn or necrosis
Dysphagia	Skin edema
Dyspnea	Skin or soft tissue (radiation) injury/tear
Endocarditis	ST segment changes
Epigastric Distress	Subclavian artery puncture
Epistaxis	Temperature elevation / Fever
Esophageal injury / perforation	Thrombocytopenia
Fatigue	Thromboembolism
Fluid overload	Thrombosis
Gastric hypomotility	Transient extremity numbness
Gastroesophageal reflux	Transient Ischemic attack (TIA)
Gastrointestinal disorders	Urinary Retention Postoperative
Gastrointestinal diverticulosis	Urinary tract injury or infection related to the urinary catheter
Gastroparesis	Valvular damage/insufficiency
Headache	Vascular (access) dissection (including coronary arteries)
Heart failure (acute or chronic)	Vascular Injury
Heart injury	Vascular occlusion
Heart valve insufficiency	Vascular Perforation
Hemoptysis	Vasovagal reactions
Hemorrhage	Ventricular Fibrillation
Hemothorax	Vessel damage/trauma
High/increased creatine phosphokinase (CPK)	Vessel perforation
Hypertension	Vessel spasm (including coronary arteries)
Hypervolemia	Visual disturbance
Hypotension	Worsening of pre-existing pulmonary disease
Hypovolemia	Wound healing disturbance

*Recurrence and exacerbation of an existing arrhythmia are anticipated adverse events. However, they will not be captured as such under this protocol, as they are considered recurrence of disease.

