15.1 Specific Safety Parameters

15.1.1 Definition of Adverse Events (AE)

An AE is any untoward medical occurrence in a subject whether or not related to the investigational device.

Specifically, an AE is **any** undesirable experience (sign, symptom, illness, abnormal laboratory value, or other medical event) occurring to a subject during the course of the study, whether or not it is related to the investigational device or procedure. Physical findings (including vital signs) observed at follow-up, or pre-existing physical findings that worsen compared to baseline are considered AEs.

Any medical condition that is present at the time that the participant is screened will be considered as baseline and not reported as an AE. Such conditions should be added to background medical history, if not previously reported. However, if the study participant's condition deteriorates at any time during the study, it will be recorded as an AE.

Arrhythmia recurrence by itself is considered a recurrence of disease (pre-existing condition), and, therefore, **does not meet the definition of an AE.**

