15.1.2 Definition of Serious Adverse Event (SAE)

A SAE is any event that meets one or more of the following criteria:

- Leads to death
- Leads to a serious deterioration in the health of a subject that resulted in:
 - A life-threatening illness or injury
 - An injury or permanent impairment of a body structure or a body function
 - In-patient hospitalization or prolongation of an existing hospitalization*
 - Medical or surgical intervention to prevent life-threatening illness or injury or permanent impairment to body structure or a body function
 - Chronic disease
- Leads to fetal distress, fetal death or a congenital abnormality or birth defect.

*Planned hospitalization for a condition present prior to the participant's enrollment in the study will not meet the definition of an SAE. An AE would meet the criterion of "hospitalization" if the event necessitated an admission to a health care facility (e.g., an overnight stay). Emergency room visits that do not result in admission to the hospital should be evaluated for one of the other serious outcomes.

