15.2.2 Relationship to Study Device

For all collected AEs, the clinician who examines and evaluates the participant will determine the AEs causality based on temporal relationship and his/her clinical judgment. The degree of certainty about causality will be graded using the categories below as described per Medical Device Regulation (MDR)

Table 5: Adverse Event Causality Classifications

Caused By	Relation	Definition of Relation
Device	Definitely (Causal Relationship)	The event is associated with the investigational device beyond reasonable doubt
	Probable	The relationship with the use of the investigational device seems relevant and/or the event cannot be reasonably explained by another cause, but additional information may be obtained
	Possibly	The relationship with the use of the investigational device is weak but cannot be ruled out completely. Cases where relatedness cannot be assessed, or no information has been obtained should also be classified as possible
	Not related	Relationship to the investigational device can be excluded
Study Procedure	Definitely (Causal Relationship)	The event is associated with the study procedure beyond reasonable doubt
	Probable	The relationship with the study procedure seems relevant and/or the event cannot be reasonably explained by another cause, but additional information may be obtained
	Possibly	The relationship with the study procedure is weak but cannot be ruled out completely. Cases where relatedness cannot be assessed, or no information has been obtained should also be classified as possible
	Not related	Relationship to the procedure can be excluded

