15.4 Reporting Procedures

15.4.1 Adverse Event Documentation and Reporting Requirements

Subjects should be encouraged to report AEs spontaneously or in response to general, non-directed questioning (e.g. “How was your health been since last visit?”). Anytime during the study, the subject may volunteer information that resembles an AE.

Each AE must be reported to the sponsor regardless of classification, seriousness, intensity, outcome or causality. The investigator is responsible for ensuring that all AEs observed by the investigator, or reported by the subject, that occur from the time that the subject has signed the informed consent through the end of the study are properly assessed, recorded, and reported as defined and described in the AEs, Adverse Device Effects and Device Deficiencies section of this protocol (section 15). All AEs must be documented by completing subject’s medical records (source documents) and appropriate eCRF by the investigator or study coordinator throughout the study and provided to the Sponsor. All AEs will be monitored until they are adequately resolved or explained.

Anonymized documentation pertaining to the AE (e.g. laboratory tests, consultation reports, post-mortem reports, new information relating to a previously reported AE, correspondence with the local EC, etc.) will be provided by the investigator to the sponsor or designee in a timely manner, when requested. Follow-up reports relative to the subject’s subsequent course must be submitted to the sponsor or designee until the event has resolved or, in case of permanent impairment, until the condition stabilizes. If the subject is withdrawn from the study because of the AE, the information must be included on the appropriate eCRFs.

The Sponsor is responsible for the classification of AEs and ongoing safety evaluation of the study and shall review the investigator’s assessment of all AEs. The sponsor will determine and document in writing their seriousness and relationship to the investigational device. In case of disagreement between the sponsor and the PIs, the sponsor shall communicate both opinions to the concerned parties.

Biosense Webster will ensure that investigators are instructed to return devices suspected of causing an AE or SAE (i.e., linked to device-related AE) in accordance with relevant regulations and current company procedures.

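### The Table 7 footnote drops exacerbation of an existing arrhythmia from adverse event capture, against section 15.1.1, and so can lower the safety counts

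*Combined protocol and SAP*

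**What the plan says.** Four places in the combined protocol and SAP bear on whether a worsened arrhythmia is an AE.

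- **Section 15.1.1, exemption.** "Arrhythmia recurrence by itself is considered a recurrence of disease (pre-existing condition"), and for that reason it falls outside the AE definition. Exacerbation is not mentioned.
- **Section 15.1.1, baseline conditions.** A condition present at screening is not an AE, but if the participant's "condition deteriorates at any time during the study, it will be recorded as an AE".
- **Section 15.2.4, Table 7.** The list of anticipated AEs, which are to be reported through EDC, has the row "Arrhythmia (new or worsening of pre-existing arrhythmia").
- **Section 15.2.4, footnote to Table 7.** "Recurrence and exacerbation of an existing arrhythmia are anticipated adverse events. However, they will not be captured as such under this protocol". The reason given is that "they will not be captured as such under this protocol, as they are considered recurrence of disease".

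Section 20.4.7 makes catheter-related serious AEs (SAEs) within 7 days the primary safety endpoint and counts every relationship grade except Not Related. Section 20.4.8 adds all SAEs and catheter-related non-serious AEs as secondary safety endpoints.

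**The concern.** The footnote's reason fits recurrence: the disease has come back. It does not fit an arrhythmia made worse during or after catheter manipulation, yet the footnote applies it to both and is silent on serious or device-provoked worsening. Such worsening is foreseeable here. Section 14.2.2 asks investigators to bookmark arrhythmias started by manipulating the study catheter and gives PVCs as the example, while VT and PVC are two of the five enrolled subgroups (section 20.4.2). A catheter-provoked arrhythmia can therefore be the subject's own study arrhythmia.

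Two things are at stake. The related-SAE count, which is the primary safety result of a first-in-human study, may be too low. And two sites that follow different passages may classify the same event differently.

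**Working it through.** The plan states no figure on this point, and the sample size of 30 rests on previous experience rather than a formula, so there is nothing to reproduce. The check is a comparison of texts, followed by an illustration of scale.

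**1. Do the passages conflict?** Take a subject enrolled with VT whose VT worsens within 7 days.

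| Passage | Outcome |
|---|---|
| 15.1.1, deterioration of a baseline condition | Recorded as an AE |
| 15.1.1, exemption | Does not apply: recurrence by itself only |
| Table 7, row on worsening | Anticipated AE, reported via EDC |
| Table 7, footnote | Not captured |

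Three lines lead to recording and one to not recording. No precedence rule is given. The footnote also removes the worsening half of the Table 7 row, whichever row its asterisk belongs to. The half on new arrhythmia survives.

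**2. Do other provisions restore the event?**

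- Section 15.1.2 is broad: "A SAE is any event that meets one or more of the following criteria". This helps, but a site told not to capture exacerbation may never reach the seriousness assessment.
- Section 15.2.2 leans towards counting: "Cases where relatedness cannot be assessed, or no information has been obtained should also be classified as possible". Section 20.4.7 leans the same way. Both act on events already recorded as AEs.
- Section 15.4.1 provides a second look: "The Sponsor is responsible for the classification of AEs and ongoing safety evaluation of the study". That review is of AEs, so it need not reach an event never entered as one.
- The bookmarks under section 14.2.2 may leave a trace, but section 20 does not summarise them.

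**3. What is the remaining gap?** New arrhythmias stay reportable. So do consequences with their own Table 7 rows, such as ventricular fibrillation, cardiac arrest, cardiogenic shock and hypotension. For the primary endpoint, what is left is a serious, possibly catheter-provoked worsening of the subject's existing arrhythmia with no separately listed consequence. An example is one that is serious only because it prolonged the hospital stay. For the secondary endpoint, it is the non-serious equivalent.

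**4. Direction.** Under section 20.4.1, AE percentages use all subjects in the analysis population. A dropped event can leave the numerator while the denominator stays fixed, so the percentage falls or stays the same.

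**5. Scale, as an illustration only.** Inputs are 30 subjects, about 20 atrial and 10 ventricular procedures (section 20.2), and the two-sided 95% level (section 20.1). Suppose one subject has such an event. With *x* subjects affected out of *n*, the Clopper-Pearson limits are the 2.5% point of Beta(*x*, *n* − *x* + 1), or 0 when *x* = 0, and the 97.5% point of Beta(*x* + 1, *n* − *x*).

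| Group | Captured | Not captured |
|---|---|---|
| All, n = 30 | 1/30 = 3.3% (0.1 to 17.2) | 0/30 = 0% (0 to 11.6) |
| Atrial, n = 20 | 1/20 = 5.0% (0.1 to 24.9) | 0/20 = 0% (0 to 16.8) |
| Ventricular, n = 10 | 1/10 = 10.0% (0.3 to 44.5) | 0/10 = 0% (0 to 30.8) |

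The chance that at least one of 30 subjects has such an event is 1 − (1 − *p*)^30. The documents give no value for *p*. For assumed values of 1%, 2%, 5% and 10% it is 26.0%, 45.5%, 78.5% and 95.8%.

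**The case against.** The best defence turns on the words *as such*. The footnote sits in a section on expectedness and could mean only that these events are not coded as anticipated. But its stated reason, that they are recurrence of disease, is the one 15.1.1 uses to put an event outside the AE definition, so the more natural reading is that the events are not recorded. At best the wording is ambiguous, and that alone invites different practice between sites.

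Second, the gap is narrow. Table 7 also lists palpitations, dizziness, dyspnea, chest pain and heart failure, so much symptomatic worsening would be reported under another term, and the by-subject count might not change. This stands: the counts fall or stay level, and the set of lost events is probably small. It is not empty.

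Third, there are other routes. Unscheduled visits for a worsened cardiovascular condition are recorded in the eCRF (section 14.5), and a safety lead and a chartered committee review safety data (section 15.5). The Safety Management Plan and the charter are not among the documents and may say more. These routes may help monitoring, but nothing in the documents adds an event found that way to the section 20 counts.

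Last, the study is descriptive, with no hypothesis test and no safety threshold. That is correct, and it limits the consequence to the reliability of the reported counts.

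**Conclusion.** The concern holds. The footnote exempts exacerbation, while section 15.1.1 and the Table 7 row would have it recorded, and no passage settles the conflict. Where the footnote is followed, the related-SAE count and the secondary AE counts can be biased downward, never upward. The size cannot be estimated from the documents. One affected subject would be worth 3.3 percentage points overall and 10 points among the ventricular procedures, enough to decide whether the report shows any related SAE. These figures assume that exactly one such event occurs, that the site applies the footnote, and that the subject has no other event that would be counted. No decision rule or sample size changes. The text should be corrected, because as written it can remove events that the primary safety endpoint is meant to count.

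**What to change.** Reconcile section 15.1.1, the Table 7 row and its footnote so that only recurrence by itself is exempt. For the cases that matter most, state that the exemption never covers worsening, or a catheter-provoked arrhythmia, that meets an SAE criterion or has any relationship grade to the study catheter except Not Related. Such events should be recorded as AEs, assessed for seriousness and relationship, and counted under sections 20.4.7 and 20.4.8. To avoid over-reporting, add that an arrhythmia present, or deliberately induced, as part of mapping is not an AE on that ground alone.

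The cost is protocol wording and eCRF guidance, a few more AE records, and possibly a less favourable safety count.

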15.3 Time Period and Frequency for Event Assessment and Follow-up

The investigator, or designated individual, will record all reportable events with start dates occurring any time after informed consent is obtained. At each study visit, the investigator will inquire about the occurrence of AEs/SAEs since the last visit.

All AEs, especially SAE's, need to be followed until the event is resolved (with or without sequelae), stabilization, or until the event is adequately explained. The medical monitor or designee of this clinical investigation will decide if more follow-up information is needed in case the event is not resolved at study completion. All required treatments and outcomes of the SAE must be recorded in the eCRF.

15.4 Reporting Procedures

15.4.1 Adverse Event Documentation and Reporting Requirements

Subjects should be encouraged to report AEs spontaneously or in response to general, non-directed questioning (e.g. “How was your health been since last visit?”). Anytime during the study, the subject may volunteer information that resembles an AE.

Each AE must be reported to the sponsor regardless of classification, seriousness, intensity, outcome or causality. The investigator is responsible for ensuring that all AEs observed by the investigator, or reported by the subject, that occur from the time that the subject has signed the informed consent through the end of the study are properly assessed, recorded, and reported as defined and described in the AEs, Adverse Device Effects and Device Deficiencies section of this protocol (section 15). All AEs must be documented by completing subject’s medical records (source documents) and appropriate eCRF by the investigator or study coordinator throughout the study and provided to the Sponsor. All AEs will be monitored until they are adequately resolved or explained.

Anonymized documentation pertaining to the AE (e.g. laboratory tests, consultation reports, post-mortem reports, new information relating to a previously reported AE, correspondence with the local EC, etc.) will be provided by the investigator to the sponsor or designee in a timely manner, when requested. Follow-up reports relative to the subject’s subsequent course must be submitted to the sponsor or designee until the event has resolved or, in case of permanent impairment, until the condition stabilizes. If the subject is withdrawn from the study because of the AE, the information must be included on the appropriate eCRFs.

The Sponsor is responsible for the classification of AEs and ongoing safety evaluation of the study and shall review the investigator’s assessment of all AEs. The sponsor will determine and document in writing their seriousness and relationship to the investigational device. In case of disagreement between the sponsor and the PIs, the sponsor shall communicate both opinions to the concerned parties.

Biosense Webster will ensure that investigators are instructed to return devices suspected of causing an AE or SAE (i.e., linked to device-related AE) in accordance with relevant regulations and current company procedures.

In the case of serious device effects and device deficiencies that could have led to SAEs, the Sponsor will determine whether the risk analysis needs to be updated and whether corrective or preventative action is required.

Timing for reporting the different types of AEs is described in table 8.

Table 8: AE Reporting Requirements

Type of Adverse Event	Reporting Requirements
Serious Adverse Events	Report to Sponsor immediately upon awareness of event but no later than 72 hours
USADE & SADE	Report to Sponsor immediately upon awareness of event but no later than 72 hours
Study device deficiency associated with an AE	Report both study device failure and AE to Sponsor immediately upon awareness of event but no later than 72 hours

Study device deficiency that could have led to a SAE *	Report to Sponsor immediately upon awareness of event but no later than 72 hours
All other Adverse Events	Report to Sponsor immediately upon awareness of event but no later than 2 weeks

* If a) suitable action had not been taken, or b) intervention had not been made or, c) if circumstances had been less fortunate.

15.4.2 Serious Adverse Events Reporting

All

- SADEs
- Investigational DD that might have led to a SAE if
 - a) suitable action had not been taken or
 - b) intervention had not been made or
 - c) if circumstances had been less fortunate, whether or not they are related to the device or procedure,
- new findings/updates in relation to already reported events.

must be reported to the Sponsor, via eCRF, **immediately upon awareness of event but no later than 72 hours** by the study site personnel.

The sponsor will ensure that investigators are instructed to return devices suspected of causing an AE or SAE (i.e., device-related) in accordance with relevant regulations and current company procedures.

In the case of serious device effects and device deficiencies that could have led to SADEs, the Sponsor will determine whether the risk analysis needs to be updated and whether corrective or preventative action is required.

The sponsor will report or ensure reporting all reportable events and updates to the reportable events to the EC (by the principal investigator) as per national or site specific requirements. Event reporting to relevant CAs for non CE-marked devices will occur by the sponsor and if indicated per local country requirements by the investigator.

